It is known that slow breathing can result in a resonance phenomenon in heart rate and blood pressure. (27, 28) This results from low frequency respiratory sinus arrhythmia (RSA), the R-R interval shortening during inspiration and lengthening during expiration. Several studies have examined the effects of traditional slow breathing techniques on heart rate variability (10-13). One systematic review investigating slow breathing in healthy subjects showed that slow breathing rates generally results in greater HRV and greater synchronous BPV. Data from studies comparing three separate meditation techniques found that all practices create prominent low frequency oscillations coupled to the slow respiratory rate (13). In addition, previous studies investigating hemodynamic changes during yogic derived, slow breathing at 0.10 Hz have found decreased blood pressure during the slow breathing period in healthy subjects, subjects with hypertension, and subjects with congestive heart failure (1,2,17-19). Thus, while these findings suggest that slow breathing may induce acute changes in hemodynamics, there is limited insight to

the full effects that reduced respiratory rates may have on control of cardiovascular function, especially in individuals with a spinal cord injury.

c) Study Rationale

The relationship between respiratory patterns and cardiovascular variability in healthy persons has been previously studied. However, the impact of SCI on the interrelationships between the respiratory and cardiovascular systems remains relatively unstudied. The loss of autonomic control in SCI may mean that slow breathing has profound effects on cardiovascular variabilities. Hence, those with SCI may represent a population that could benefit from the potential physiologic effects of numerous yogic-based breathing patterns that can be applied anywhere any time. Hence, it is important to determine if slower breathing patterns can shift the cardiovascular control pattern towards important healthful effects. This physiological study will compare the effects of uncontrolled breathing and traditional yogic slow-breathing practices on cardiovascular variabilities in SCI patients.

2. Specific Aims and Objectives

***Objective 1:** To determine if those with spinal cord injury can successfully perform slow yogic breathing patterns and gain respiratory fitness with daily practice.*

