***Hypothesis 1:** Two weeks of at-home practice will result in better performance of respiratory control (maintenance of frequency and volume over time) in those who practice more, however, accurate performance of yogic breathing will be lesser in those with high thoracic injuries (T3-T6).*

***Objective 2:** To assess the respiratory and hemodynamic changes that accompany slow yogic breathing in spinal cord injury patients.*

***Hypothesis 2:** Respiratory rate will decrease, blood pressure will decrease, tidal volume will increase, and minute ventilation will remain unchanged during yogic slow breathing compared to spontaneous breathing.*

***Objective 3:** To discern the changes in the relationship between respiration, heart rate and blood pressure variabilities with yogic breathing.*

***Hypothesis 3:** Slow yogic breathing will shift the relationship between heart rate and blood pressure variabilities toward more synchronized heart rate and systemic blood pressure fluctuations.*

3. General Description of Study Design

This study will be a small (N= 20) prospective cohort study with a one-time unblinded intervention of 4 differing breathing techniques compared to paced breathing. Participants will receive a log for at-home practice and instruction lasting 45 minutes around D1 and D7 with the option to have on coaching session via MGB's Zoom application. On D14 the participant will be asked to sequentially execute the randomized breathing techniques. The lab visit will last approximately 1.5 hours, during which beat-by-beat

cardiovascular variables and breath-by-breath respiratory variables will be recorded while slow breathing. The total in-person time commitment is about 4 hours (**Figure 2**).

[figure not shown]

Figure 2: Study schema with a timeline of participant contact hours and days. There will be two moments of coached practice during a period of two weeks with at-home practice encouraged throughout the period. At the conclusion of the two weeks the breathing practices will be repeated in the laboratory while obtaining respiratory and cardiovascular measurements. *It is possible for the participants to schedule the second visit via MGB's Zoom application.

4. Subject Selection

a) Inclusion/Exclusion Criteria

We will complete studies on 20 individuals — men and women aged 18 to 60 years — with a spinal cord injury. A detailed medical history will be taken, and subjects will be selected based on the following:

Inclusion criteria:

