Two weeks after inclusion, the subjects will return to the cardiovascular laboratory for assessments. All subjects will be instructed to abstain from vigorous exercise for 1 day prior to each study to avoid autonomic and neuroendocrine effects of exercise. In addition, subjects will refrain from caffeine and alcohol for the previous 24 hours and be studied at least 2 hours after a meal. All breathing patterns and techniques will be practiced with the participant before the day of measurement and the participant will also be coached by a pre-recorded audio track during measurement.

Measurements

1) Pulmonary function test

All subjects will perform standard spirometry for spinal cord injury, as describe in (44). The same technician will test all subjects. Subjects will be seated with belts or pant waists loosened and with a nose clip. The maneuver will be demonstrated, and instructions will be given to inhale completely and "blast" the air out. The subject will be encouraged to exhale maximally and sustain the effort at least 6 sec or longer, if possible, depending on the ability and willingness of the subject to continue. The volume-time curve will be recorded on a kymograph, and the flow-volume loop will be electronically displayed for review. An acceptable effort will be a minimum exhalation time of 6 sec with a rapid start and a well-defined early peak in flow that is smooth and continuous. Three acceptable efforts will be obtained.

2) CV Lab Measurement

Throughout the protocol, subjects will lie 30° supine and will be instrumented with a 5-lead EKG, pulse oximeter, finapress with sphygmomanometer, doppler, chest and abdominal belts, a microphone and a face mask with a two-way respiratory valve; for measurements of QRS-complex, SpO₂,

beat-by-beat arterial pressure, brachial blood flow, respiratory excursions, ujjayi sound mixed expired CO₂, ventilation and end-tidal CO₂.

After instrumentation and calibration, the subject will undergo a period acclimation with a resting breathing pattern for ~7 minutes. We will then record the breathing techniques for ~7 minutes each. Other than the acclimation period with resting breathing frequency the order of the other 5 breathing patterns will be randomized. Upon completion subjects will be asked to turn-in their two-week breathing logs. Participants will proceed to perform an exit-PFT and will then be finished with their contribution to the study.

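### Hypothesis 2 uses spontaneous breathing as its reference, but the only such period at Visit 3 is the acclimation block, which is always first and not clearly recorded

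*Combined protocol and SAP*

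**What the plan says.** The comparator is named in three places, and they do not agree.

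- Section 1 c), Study Rationale: "This physiological study will compare the effects of uncontrolled breathing and traditional yogic slow-breathing practices".
- Section 2, Hypothesis 2, names its reference in its last clause: "minute ventilation will remain unchanged during yogic slow breathing compared to spontaneous breathing". Its predictions for the other variables, including the fall in pressure, are made against that same reference.
- Section 3: a "one-time unblinded intervention of 4 differing breathing techniques compared to paced breathing".

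The Visit 3 sequence is in Section 6 b), CV Lab Measurement. After instrumentation and calibration, "the subject will undergo a period acclimation with a resting breathing pattern for ~7 minutes". The next sentence is "We will then record the breathing techniques for ~7 minutes each". On order: "Other than the acclimation period with resting breathing frequency the order of the other 5 breathing patterns will be randomized".

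No later resting block, washout or repeat baseline is described. The baseline measurement at Visit 1 is a pulmonary function test, so it supplies no resting blood pressure recorded under the same conditions. Section 9 b) plans within-subject t-tests or Wilcoxon tests, with regression adjustment for age, BMI, time since injury and level of injury. It has no term for block position or time.

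**The concern.** A within-subject comparison is protected against time effects only if both conditions can fall at any point in the session. Here the reference named in Hypothesis 2 can occur only in position 1, directly after the mask, cuff and belts are fitted, in a block that the protocol itself calls acclimation. Randomising the other five patterns balances time among those five. It does nothing for a contrast with the block that always comes first.

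The predicted fall in blood pressure is exposed to this. If pressure drifts down over the session for any reason, the yogic blocks will look lower than the resting block even if breathing has no effect. If pressure drifts up, a real fall may be hidden.

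There is also a prior question. The text speaks of recording the techniques after acclimation and never says that acclimation itself is recorded. If it is not, the contrast in Hypothesis 2 cannot be computed at all.

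**Working it through.** The plan states no power, significance level, effect size or SD, and it does not derive N = 20, so there is no figure to reproduce. The check has three parts.

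**1. Position of the reference (from the documents).** Rest is in position 1 in every session. The five other patterns occupy positions 2 to 6 in random order.

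- Mean position of any one technique: (2 + 3 + 4 + 5 + 6)/5 = 4.
- Mean lag behind rest: 4 − 1 = 3 blocks, or 3 × 7 = 21 minutes.
- Range of lag: 1 × 7 = 7 to 5 × 7 = 35 minutes, ignoring gaps between blocks.
- Rest precedes the technique in 100% of orders. A comparator inside the randomised set precedes it in 50%, with a mean lag of 0.

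**2. What a given drift would do (illustration).** Assume no true breathing effect, N = 20, a paired t-test at two-sided 5%, a mean drift *d* between the resting and technique blocks, and an SD *s* of the paired difference. The level, *d* and *s* are all assumptions. The non-centrality is δ = d / (s/√20), and the critical value on 19 df is 2.093. For d = 2 and s = 8, δ = 2/(8/4.472) = 1.118, which gives a rejection probability of 18.6%.

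| Drift (mmHg) | SD 6 | SD 8 | SD 10 |
|---|---|---|---|
| 0 | 5% | 5% | 5% |
| 1 | 11% | 8% | 7% |
| 2 | 29% | 19% | 14% |
| 3 | 56% | 36% | 25% |
| 5 | 94% | 76% | 56% |

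From 2 mmHg upwards almost all of these rejections are in the direction of the drift.

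A simulation (20,000 runs, SD 8, total downward drift of 4 mmHg over the session) compared the two possible references:

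- Against the fixed first block, the bias was −2.4 mmHg with 25% false falls if the drift is linear. It was −3.5 mmHg with 47% if the drift is early and exponential, with a time constant of one block.
- Against a comparator inside the randomised order, the bias was about 0. The two-sided error rate stayed between 4.8% and 5.3% for drifts of 0 to 6 mmHg.

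**3. Can the analysis separate drift from effect?** The Section 9 covariates do not change within a session, so they cannot absorb a time effect. A position term could be estimated from positions 2 to 6, but because rest occurs only in position 1, the step from 1 to 2 has to be extrapolated. Take the exponential drift of 4 mmHg above:

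- True first step: 4 × (1 − e⁻¹) = 2.5 mmHg.
- Change from position 2 to position 6: 4 × (e⁻¹ − e⁻⁵) = 4 × (0.368 − 0.007) = 1.4 mmHg, or 1.4/4 = 0.36 mmHg per step.

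A straight line through positions 2 and 6 would therefore credit 0.36 of the 2.5 mmHg to drift and leave the rest in the breathing effect. Nothing in the planned data would show that this was wrong.

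**The case against.** The strongest reply is that Section 3 already names a paced comparator. Four techniques plus paced breathing makes five, which matches the number of randomised patterns, so a time-balanced contrast probably exists. That is right as far as it goes. Yogic-versus-paced contrasts would not be affected, and this lowers the severity. But it is an inference: Section 6 does not list the five patterns, and Section 5 describes the randomisation as applying to the yogic techniques without mentioning pacing. The paced frequency is not given either; Section 6 a) gives only a range of 0.25 to 0.08 Hz across techniques. Nor is paced breathing the reference that Hypothesis 2 names.

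It can also be said that no drift is documented, and that with a small one the error rate stays close to nominal (7–11% at 1 mmHg). Both statements are correct. The percentages show sensitivity and do not predict what will happen. Finally, this is a small physiological study with no declared primary endpoint, so a limitation that is openly reported may be tolerable. That too stands, provided that the comparator is settled and the limitation is stated.

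A reader might infer that settling will bias the result towards the hypothesis. The documents do not support that, because they give no sign for the drift. A reader might also infer that no analysis could ever separate the two. A trend model could, but only on an assumption that the data cannot test.

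**Conclusion.** The point holds as a structural one. Either Hypothesis 2 has no recorded reference, or its reference is aliased with time since instrumentation, by about 21 minutes on average. The documents also disagree on which comparator the study uses. None of this depends on an assumed number. The size of any resulting error does: it rests on an assumed drift, an assumed SD of 6 to 10 mmHg and an assumed two-sided 5% level, and runs from little above 5% to 94% over the drifts shown.

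The point is limited to the Hypothesis 2 contrast with spontaneous breathing. It is tempting to extend it to heart rate or to the synchrony prediction in Hypothesis 3. The documents do not support that: Hypothesis 2 predicts nothing about heart rate, Hypothesis 3 names no spontaneous reference, and nothing in the protocol says that regular pacing in itself raises synchrony. Severity: should-fix.

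**What to change.** 1. **Reconcile the comparator.** List the five randomised patterns, confirm that paced breathing is one of them and state its frequency. Make it the main comparator for the blood-pressure and ventilation tests under Hypothesis 2, and reword the hypothesis and the Rationale to match. State whether the acclimation block is recorded. Report yogic versus spontaneous as descriptive, with the time confounding stated. No new data are needed, but this is more than an edit: it changes the question from spontaneous to paced breathing after some sessions have been completed, and the amendment should say so.

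2. **Preferably, add a reference that can carry the spontaneous contrast.** In remaining sessions, and in the repeat Visit 3 sessions already planned for earlier participants, use the first block for acclimation only. Put a separate, recorded spontaneous block of about 7 minutes into the randomised order and include block position in the model. A spontaneous block placed only at the end is weaker, because it would mix drift with carry-over from the five patterns before it.

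The cost of the second step is about 7 minutes in a visit of roughly 90. Breathing blocks would rise from 6 × 7 = 42 to 7 × 7 = 49 minutes, leaving 90 − 49 = 41 for instrumentation, calibration and the exit pulmonary function test. The length of the exit test is not stated. If it took the 30 minutes or so given for the baseline test, 11 minutes would remain, so the visit length may need revising. Sessions already completed without such a block, and not repeated, can support the spontaneous contrast only descriptively.

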- 1) History of Spinal Cord Injury
- 2) Age: 18-60 years old
- 3) Wheelchair user
- 4) Medically stable & able to follow directions
- 5) Body mass index (18.5 - 35 kg/m²)

Exclusion criteria:

- 1) BP >140/90 mmHg
- 2) Current use of tobacco or cardioactive medications (except medication to support blood pressure)
- 3) Significant arrhythmia
- 4) Coronary artery disease
- 5) Diabetes
- 6) Renal Disease
- 7) Cancer
- 8) Epilepsy or other neurological diseases
- 9) Non-English Speakers

Source of subjects and recruitment methods

All volunteers will be considered regardless of race, ethnicity, or national origin. We plan to study both men and women. We will recruit individuals with a spinal cord injury from the Exercise for Persons with Disabilities (ExPD) program at Spaulding Hospital Cambridge.

Research Assistants will identify eligible individuals during scheduled ExPD workout sessions and from population of past ExPD participants. Where possible eligible individuals will be given a flyer. If the ExPD population is exhausted before reaching our desired number of participants, recruitment can be extended to the general SCI population of Boston via the use of flyers. If eligible and interested participants will be asked to complete a pre-screening phone survey.

5. Subject Enrollment

The principal or co-investigators will obtain volunteer consent in accordance with guidelines established by the Institutional Review Board during the first study visit to the Cardiovascular Laboratory. Participants are encouraged to ask questions and are reminded that participation is strictly voluntary and will not affect their current or future care at Spaulding Rehabilitation Hospital or any of its affiliates. Each subject will be told that he/she will be free to discontinue participation in the experiment at any time and that the investigators reserve the right to discontinue the research protocol at any time. A copy of the signed informed consent form will be given to the subject. All study subjects will participate in the same study protocol, differing only by the randomization of the order of the yogic breathing techniques.

6. Study Procedures

a) Study Components

YOGIC BREATHING INTERVENTION

The subject will receive one-on-one coaching on breathing techniques with the co-investigator two times. The subject may opt to complete the second coaching session via MGB's Zoom application.

The breathing techniques will be varied in:

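### No balancing of the order of the five breathing patterns is described and the analysis has no position term; a Williams design fits N=20 exactly and, with a position term, would sharpen every pattern contrast

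*Combined protocol and SAP*

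**What the plan says.** Section 3 describes a "small (N= 20) prospective cohort study" of "4 differing breathing techniques compared to paced breathing", which makes five conditions. It adds that "On D14 the participant will be asked to sequentially execute the randomized breathing techniques". Section 4 plans to complete 20 people.

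Section 6 (Visit 3, CV Lab Measurement) puts a resting acclimation period of about 7 minutes first. It then says "We will then record the breathing techniques for ~7 minutes each" and "Other than the acclimation period with resting breathing frequency the order of the other 5 breathing patterns will be randomized". Section 5 says that participants follow one protocol, "differing only by the randomization of the order of the yogic breathing techniques".

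No section says how the orders are generated: there is no sequence list, no restriction and no named design. Section 9 compares means within subjects by t-test or Wilcoxon test and lists age, BMI, time since injury and level of injury as covariates. Position, sequence and the preceding pattern do not appear.

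**The concern.** Five patterns of about 7 minutes run one after another for about 35 minutes. Blood pressure and ventilation could drift over that time through settling, fatigue or instrument drift. If one pattern happens to fall late more often than another, part of the drift enters the contrast between them.

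There are 120 possible orders and only 20 people, so independent draws cannot be relied on to even this out. As written, neither the allocation nor the analysis controls a session trend. What is at stake is the precision of every pattern contrast in a small study that has blood pressure change among its hypotheses.

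**Working it through.** The plan gives no figure for order balance, so there is nothing to reproduce.

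**Inputs from the documents.** 20 participants (Sections 3 and 4); 4 techniques plus paced breathing = 5 patterns (Section 3), matching the 5 in Section 6; no position term (Section 9).

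**Assumptions not in the documents.** Orders drawn independently; linear drift of 0, 1 or 2 mmHg per position; SD of a paired difference without drift of 6 mmHg.

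**1. Spread over positions.** The count of a given pattern in a given position is Binomial(20, 1/5), with mean 4; P(exactly 4) = 0.218. In 200,000 simulated studies of 20 independent orders:
- exact balance over all 25 cells: 0 studies
- some cell 8 or more: 56%
- some cell 1 or fewer: 84%
- some pattern never in some position: 25%

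**2. Mean position.** Within a person each position has variance 2, and two patterns' positions have covariance −0.5. The variance of their difference is 2 + 2 + 1 = 5. Over 20 people the SD of the mean difference is √(5/20) = 0.50 positions. The largest of the four differences from paced breathing has median 0.65 and reaches 1 position or more in 16% of studies.

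**3. Effect on a contrast.** With drift d, the variance of one paired difference is 36 + 5d², and the SE of the mean is its square root over √20.

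| Drift (mmHg per position) | Variance | Rise | SE (mmHg) | Rise in SE |
|---|---|---|---|---|
| 0 | 36 | 0% | 1.34 | 0% |
| 1 | 41 | 5/36 = 14% | 1.43 | 7% |
| 2 | 56 | 20/36 = 56% | 1.67 | 25% |

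Equivalently, the chance shift in a contrast has SD 0.5 mmHg at d = 1 and 1.0 mmHg at d = 2. This is the same effect expressed another way, not an additional one. In simulation the paired t-test under independent orders kept a type I error of about 5% at both drifts.

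**4. The balanced alternative.** For five patterns a Williams design needs a pair of 5×5 squares, 10 sequences in all: 01423, 12034, 23140, 34201, 40312 and their reversals. Used twice it takes 20 people. Each pattern is then in each position 4 times, and each ordered pair of neighbours occurs 20 × 4 / 20 = 4 times. A single 5×5 Latin square balances position, but none of the 1,344 enumerated (first column fixed) balances neighbours.

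**5. Balance with the paired test unchanged.** The drift cancels from the mean contrast, so its true variance is 36/20. It stays in each person's difference and therefore in the estimated SE. In the sequences above, the mean squared position difference is 2.8 for half the pairs (patterns 0 and 1: (1+4+4+1+4)/5) and 7.2 for the rest (patterns 0 and 2: (9+1+16+1+9)/5). At d = 2 the expected sample variance is 36 + 4 × 2.8 × 20/19 = 47.8 or 36 + 4 × 7.2 × 20/19 = 66.3, against the 36 that applies. Simulated type I error was about 2.5% and 0.9% respectively, so the test is conservative. With subject, pattern and position in the model it returned to about 5%.

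**6. What balance adds to a position term.** With categorical position in the model, independent orders gave a contrast variance about 6% above the balanced design on average, or about 3% in SE (√1.06 = 1.03).

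**The case against.** A reader might infer that the plan uses unrestricted randomisation. The documents do not say so. They are silent on the method, and a Latin or Williams square with random assignment would also be a randomised order. The figures on uneven spread hold only if the orders are drawn independently; if a balanced list already exists, stating it settles that part.

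A reader might also infer that the contrasts are biased. They are not: the error averages zero over the randomisation, and the paired SE already contains it.

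The size depends on drift that the documents do not give. The acclimation period may reduce early settling, and with no drift nothing is lost. A position term alone would recover most of the loss, so balancing by itself is a refinement. Nor can it be said that balancing removes the problem without further change, since under the Section 9 tests it leaves the drift in the SE.

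Exact balance also needs 20 complete sessions, and Section 6 shows that some Visit 3 sessions may predate the current version.

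All of this stands. It limits the size of the point and makes the model term part of the remedy. It does not remove the gap: no allocation method and no position term are stated, and both are easily supplied.

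**Conclusion.** The point holds as an inexpensive gain in precision, not as the correction of an invalid design. On independent orders, uneven spread is almost certain. The cost is 0%, 14% or 56% in contrast variance at 0, 1 or 2 mmHg of drift per position, given an assumed paired-difference SD of 6 mmHg. Most of that is recovered by a position term, and balancing adds about 6% in variance on top.

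Two limits apply. A common position term removes average drift, not differences in drift between people. And balancing does nothing for a comparison with the resting acclimation period, which always comes first; if that recording is the spontaneous-breathing reference in Hypothesis 2, the order confounding there remains.

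**What to change.** **Section 6.** State that participants are assigned at random to the 10 sequences of a five-pattern Williams design, 2 per sequence for N=20, and that paced breathing is one of the five patterns. Bring Section 5, which speaks only of the yogic techniques, into line. If only four patterns are meant to be randomised, a four-sequence Williams square used 5 times also gives 20.

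**Section 9.** Compare patterns with a model containing subject, pattern and position in place of separate paired tests. With 20 × 5 = 100 observations and 20 + 4 + 4 = 28 parameters, 72 residual degrees of freedom remain.

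**Sessions already done.** Keep the orders used and assign the remaining participants so that the position counts come as close to equal as possible. Say which session is analysed for people who repeat Visit 3, and do not pool first and repeat sessions to complete the balance.

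**Cost.** One order list, a sentence in each section and one model term. Balance will be approximate where sessions are already done or incomplete; the position term then does most of the work.

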1. breath frequency (between 0.25 and 0.08 Hz)
2. Inspiratory – Expiratory ratio (I:E) or 'Duty Cycle'
3. with and without ujjayi (yogic throat constriction)
4. with and without inspiratory/expiratory breath holding

AT-HOME PRACTICE

At the end of the first visit the subject will be given a log to record their at-home practice of the breathing techniques they were coached on. Participants will also receive an information pamphlet and audio track with information about the exercises covered during the first coaching session.

b) Study Visits

Pre-Screening

All study subjects from the ExPD program at Spaulding Hospital will be preliminarily screened over the telephone to ensure that they meet preliminary eligibility requirements. Eligible members will be approached after their workouts by the co-investigator to ask permission to call for screening.

Screening

Subjects who meet preliminary eligibility criteria and are interested in participating will be called by the co-investigator to screen inclusion and exclusion criteria and to discuss additional information about the study. Participants will be sent the informed consent letter at least one week before the first visit. Informed consent will be obtained at Spaulding Rehabilitation Hospital, Cambridge.

Visit 1 — History, Baseline, 1st Coaching

During participants first visit the study procedures will be reviewed in detail with study staff, the subject will give a detailed health history and their written informed consent to the principal or co-investigator. The participant will then proceed to complete a baseline pulmonary function test (PFT) lasting about 30 minutes. Leaving about 45 minutes to cover relevant breathing techniques and exercises.

Visit 2 — 2nd Coaching

The second coaching visit can optionally be completed via MGB's Zoom application and will be shorter and more focused on questions, concerns, or struggles of the participant.

Visit 3 — Breathing & Measurement

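### The home-practice log, the only practice measure described for Hypothesis 1, is handed in after the Visit 3 breathing recordings, leaving an avoidable opening for late entries

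*Combined protocol and SAP*

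**What the plan says.** Section 2, Hypothesis 1, predicts: "Two weeks of at-home practice will result in better performance of respiratory control (maintenance of frequency and volume over time) in those who practice more". The exposure is the amount of practice; the outcome is respiratory control.

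Section 6, At-Home Practice, supplies the only instrument for that exposure. At the end of Visit 1 "the subject will be given a log to record their at-home practice of the breathing techniques they were coached on".

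Section 6, Visit 2, describes the next contact: "The second coaching visit can optionally be completed via MGB's Zoom application and will be shorter and more focused on questions, concerns, or struggles". It mentions no review of the log.

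Section 6, Visit 3, CV Lab Measurement, gives the order of the day. After instrumentation and a resting period, "We will then record the breathing techniques for ~7 minutes each". The hand-in comes next: "Upon completion subjects will be asked to turn-in their two-week breathing logs". The visit then closes: "Participants will proceed to perform an exit-PFT and will then be finished with their contribution to the study".

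Section 9 neither lists the log among the variables collected nor gives an analysis of practice against performance. Section 10 sets up no formal quality-assurance programme.

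**The concern.** A self-reported exposure is best fixed before the outcome is observed. Here the log stays in the participant's hands until the breathing recordings are finished. A participant with gaps in the log could fill them, or alter entries, after a session that felt easy or hard. Reported practice would then depend partly on performance, and an association could appear, shrink or reverse for reasons unrelated to any effect of practice.

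The practice half of Hypothesis 1 is at stake. The log is the only source described for it, so there is no second measure to check it against.

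**Working it through.** The point concerns the order of procedures. The plan states no figure to reproduce: it gives N = 20 without alpha, power, effect size or SD.

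**Order of events, from Sections 2 and 6**

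1. End of Visit 1: log issued.
2. Visit 2, around day 7, possibly remote: no log check described.
3. Visit 3: instrumentation, resting period, then five patterns in random order. Six recordings of about 7 minutes give 6 × 7 = 42 minutes.
4. Log handed in.
5. Exit pulmonary function test.

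Step 3 generates the Hypothesis 1 outcome and step 4 closes the exposure, so the exposure is open while the outcome is produced. Step 5 follows the hand-in, so the exit pulmonary function test is not affected.

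**What the participant can know.** The documents describe no feedback of results. They do say that "the participant will also be coached by a pre-recorded audio track during measurement", so a participant can sense whether they kept to the pattern. That is a cue to performance, not knowledge of the measured result.

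**Illustration of size, under assumptions not in the plan.** Assume that true practice P and performance Y are independent with unit SD, that n = 20, and that a two-sided Pearson test is run at 5%. Let reported practice be P + bY. The induced correlation is r = b/√(1 + b²), and the share of variance in the log due to late changes is r². The critical value is |r| = t/√(n − 2 + t²) with t = 2.101 on 18 degrees of freedom, which gives 2.101/√(18 + 4.414) = 0.444. Rejection rates come from 200,000 simulated studies per value of b.

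| b | induced r | r² | rejection rate |
|---|---|---|---|
| 0 | 0.00 | 0.00 | 5.0% |
| 0.1 | 0.10 | 0.01 | 7.0% |
| 0.2 | 0.20 | 0.04 | 13.1% |
| 0.3 | 0.29 | 0.08 | 23.4% |
| 0.5 | 0.45 | 0.20 | 53.0% |

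A negative b gives the same two-sided rates by symmetry, with the association in the opposite direction to Hypothesis 1. The documents give no basis for choosing b, in size or sign. The table shows only what a given shift would do at this sample size.

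**The case against.** The strongest reply is that the log is a diary, not a recall questionnaire. It is issued at Visit 1 for use over two weeks, and the text says it is turned in at Visit 3, not completed there. The participant is masked and instrumented during the recordings and goes on to the exit test afterwards. Section 10 has participants watched throughout, so the window for changes is short and not private. This stands as a reason to expect any effect to be small. It does not justify the present order, and the protocol gives no reason for collecting the log last.

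Four stronger readings are tempting, and the documents do not support them.

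- A reader might infer that participants know how well they performed. No results are fed back; they have only their own sense of the session.
- A reader might infer that the bias favours Hypothesis 1. Someone who did well might add practice, but someone who struggled might also over-report to show effort. The sign is not established.
- A reader might take the larger rejection rates as the plan's error rate. They follow from a chosen b and a test that Section 9 does not contain. At b = 0.5, one fifth of the variance in a two-week log would have to come from late changes, which is hard to credit for a diary already mostly filled in.
- A reader might infer that Visit 2 rules out a log check, or that the coach is present at hand-in. The Visit 2 text describes an emphasis and excludes nothing, and nobody is named as present at hand-in.

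It is also fair to say that the missing practice–performance analysis in Section 9 is a larger gap than the timing of the log. If entries prove to be dated, week 1 could be examined separately, so the problem is not necessarily beyond repair in analysis.

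**Conclusion.** The point holds as a minor, low-cost improvement. The text explicitly places collection of the log after the recordings, and it describes no earlier check or closing rule. This leaves an avoidable opportunity for outcome-dependent reporting in the only practice measure described. The documents do not show that it happens. Its size and direction are unknown, and the effect may be nil.

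The conclusion rests on two inferences: that the log is the Hypothesis 1 exposure, since no other practice measure is described, and that participants can sense how the session went. It applies to the Visit 3 breathing recordings only, not to the exit pulmonary function test or to Hypotheses 2 and 3.

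**What to change.** - Amend the Visit 3 text in Section 6 so that the log is collected, dated and closed on arrival, before instrumentation.
- At Visit 2, have staff copy or photograph the entries to date, or have them shown on the video call, so that week 1 is on record.
- State that the practice–performance analysis uses only entries made before the Visit 3 recordings.
- Flag logs already collected after the recordings. The note at the end of Section 6 shows that some participants may have completed Visit 3 before 5/19/23, and the change cannot be applied to their logs.

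The cost is protocol wording and a minute or two of staff time, with the same form at the same visits. The change does not stop a participant back-filling the log before arrival, although the Visit 2 copy limits this for week 1.
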